14.6 Safety

The assessment of safety will be based mainly on the frequency of adverse events (AEs) that are treatment-emergent (TEAEs). Formal statistical tests will not be conducted for differences in safety parameters between treatment groups.

The incidence of all treatment-emergent AEs will be tabulated after grouping by system organ class and preferred term. For each preferred term and summarized over each system organ class overall, the table will present the absolute number and proportion (%) of patients in each treatment group in whom the event occurred. The incidence of all suspected-IMP-related AEs will be tabulated similarly. The incidence of all treatment-emergent AEs will also be tabulated by severity categories.

Safety will also be summarized with respect to vital signs as mean levels by visit and change from baseline. Abnormal observations on physical examinations will be listed.

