5.4 Safety Outcomes

The study will evaluate the safety of rhC1INH in the setting of COVID-19 infections if added to SOC compared to SOC treatment only by measuring the incidence of adverse events up to 3 months post-treatment.

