9.2 Procedures at Each Visit

9.2.1 Split into Subtitles by Type of Visit

Visit 1, Screening (Day -1)

Informed consent will be obtained before any study-specific tests or evaluations will be performed.

- Patients who are admitted to the hospital with confirmed SARS-CoV-2 infection will be screened. Screening will be based on routinely available data and laboratory tests with only the pregnancy test as study-specific intervention/test, if necessary, before screening of the patients. Results from prior tests that will be used for screening potentially eligible subjects will be recorded in the CRF.
- Selection of potential participants according to inclusion and exclusion criteria.
- Explanation of patient information including study purpose and signature of informed consent form
- Assessment of demographics, medical history, physical examination, and concomitant medication history
- Pregnancy test if applicable
- Eligibility check (in- and exclusion criteria)
- Study enrollment

Visit 2, Intervention period (Day 0)

- Randomization
- Assignment of the trial subject identification number
- Assessment of physical examination and concomitant medications
- Assessment of vital signs including respiratory rate.
- Assessment of WHO Ordinal Scale and need for oxygen supplementation
- Collection of blood (15ml) for analysis of ferritin, IL-6, D-Dimer, C1INH concentration, and collection of blood for the analysis of complement proteins (C3 & C4).
- Routine full blood count, coagulation and biochemistry studies will only be performed.
- Virology testing (SARS-CoV-2 PCR) on a nasopharyngeal sample if not already performed before inclusion into the study
- Following randomization, participants in the active treatment group will receive rhC1INH (150 U/ml) at a 50 U/kg dose (max dose of 4200 U) every 12 hours, as a slow intravenous injection in approximately 5 minutes. The time of dosing and the dose will be recorded.
- AEs occurring after the administration will be recorded.
- Routine laboratory tests will be performed daily during admission according to standard procedures, and should include a set of hematology, coagulation and biochemistry parameters. Additionally, blood (7ml) for analysis of ferritin, IL-6, D-Dimer, C1INH concentration will be collected at the same time point.
- Monitoring of prolonged QT intervals in severely-ill subjects receiving multiple drugs.
- Measurement of oxygenation levels.

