11.4 Planned Analyses

11.4.1 Datasets to be Analysed, Analysis Populations

A review of the database will be conducted in a blinded manner shortly before the database will be locked, and any decisions made at that meeting (blinded Data Review Meeting) concerning the statistical analysis, e.g., additional outcomes and populations, pooling of sites for efficacy analysis, will be documented in the Statistical Analysis Plan (SAP).

Missing data for the primary endpoint will be imputed by means of the Last-observation-carried-forward (LOCF) method, as sensitivity analyses some alternative imputation methods like imputation of the mean and multiple imputation will be additionally performed.

Safety Population: The Safety Population is defined as all patients who received at least one dose of rhC1INH. Statistical analyses will be based on the actual treatment the patient received.

Full Analysis Set/Intent-to-Treat Population: The FAS/ITT Population is defined as all patients who are randomly allocated to a study arm. Statistical analyses will be based on the treatment arm to which the patient was allocated. For quantitative data, the number of patients with non-missing information, means, medians, standard deviations and extremes will be determined. For qualitative data, absolute and relative frequencies will be calculated. Moreover, changes from baseline (V2, d0) will be calculated.

Per Protocol Population: The PP Population is defined as all patients in the FAS/ITT Population who complete the study and who do not have any major protocol violations, including the following:

- Patients who had major inclusion/exclusion criteria violations.

Sufficient compliance is expected because of IV administration of the IMP.

The PP Population will be determined by a blinded review in the Data Review Meeting (DRM) of the data prior to database lock. The primary efficacy analysis will be based on the FAS/ITT Population in this superiority trial; an additional efficacy analysis will be performed on the PP Population. The Safety Population will be used for all safety analyses.

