5.6 Derived variables

For quantitative variables the absolute changes from baseline (Visit 2) will be determined.

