14.2 Datasets to be analyzed, Analysis populations

A review of the database will be conducted in a blinded manner shortly before the database will be locked, and any decisions made at that meeting (blinded Data Review Meeting) concerning the statistical analysis, *e.g.*, additional outcomes and populations, pooling of sites for efficacy analysis, will be documented in the Statistical Analysis Plan (SAP).

Missing data for the primary endpoint will be imputed by means of the Last-observation-carried-forward (LOCF) method, as sensitivity analyses some alternative imputation methods like imputation of the mean and multiple imputation will be additionally performed.

The following analysis populations will be used for analysis of study data:

Safety population: The Safety Population is defined as all patients who received at least one dose of rhC1-INH. Statistical analyses will be based on the actual treatment the patient received.

Full Analysis Set (FAS)/Intention to treat (ITT) population: The FAS/ITT Population is defined as all patients who are randomly allocated to a study arm. Statistical analyses will be based on the treatment arm to which the patient was allocated. For quantitative data, the number of patients with non-missing information, means, medians, standard deviations and extremes will be determined. For qualitative data, absolute and relative frequencies will be calculated. Moreover, changes from baseline (V2, d0) will be calculated.

Per protocol (PP) population: The PP Population is defined as all patients in the FAS/ITT Population who complete the study and who do not have any major protocol violations, including the following:

- Patients who had major inclusion/exclusion criteria violations.

Sufficient compliance is expected because of IV administration of the IMP.

The PP Population will be determined by a blinded review in the Data Review Meeting (DRM) of the data prior to database lock. The primary efficacy analysis will be based on the FAS/ITT Population in this superiority trial; an additional efficacy analysis will be performed on the PP Population. The Safety Population will be used for all safety analyses.

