14.6.1 Adverse events

Adverse events will be coded according to MedDRA. The assessment of Safety will be based mainly on the frequency of AEs that are treatment emergent (TEAEs). Formal statistical tests will not be conducted for differences in safety parameters between treatment groups.

The incidence of all treatment-emergent AEs will be tabulated after grouping by system organ class and preferred term. For each preferred term and summarized over each system organ class overall, the table will present the absolute number and proportion (%) of patients in each treatment group in whom the event occurred. The incidence of all suspected-IMP-related AEs will be tabulated similarly. The incidence of all treatment-emergent AEs will also be tabulated by severity categories.

Safety will also be summarized with respect to vital signs as mean levels by visit and change from baseline. Abnormal observations on physical examinations will be listed.

Summary statistics for the absolute vital sign value and the changes from baseline will be presented using n, mean, standard deviation, median, minimum, and maximum.

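### Blood pressure and heart rate are kept as one undirected daily worst value and summarised without counts, so the number of patients with low or high values is not shown and, read literally, standard-of-care patients are left out

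*SAP*

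**What the plan says.** **What is recorded.** SAP 5.3 lists heart rate, respiratory rate, temperature, systolic and diastolic blood pressure and SpO2 at Visits 2 to 6. In Protocol 9.1 and SAP 5.8, footnote 7 on the vital-signs row says that the worst value on a given day is the one documented. Neither document defines worst for blood pressure or heart rate.

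**How it is summarised.** SAP 14.6: "Safety will also be summarized with respect to vital signs as mean levels by visit and change from baseline". SAP 14.6.1: "Summary statistics for the absolute vital sign value and the changes from baseline will be presented using n, mean, standard deviation, median, minimum, and maximum". Protocol 11.4.5 has the same plan. SAP 5.6 adds: "For quantitative variables the absolute changes from baseline (Visit 2) will be determined". No limit, shift table or count of low or high vital signs appears. The only listing of abnormal observations covers physical examinations.

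**In whom.** SAP 14.2: "The Safety Population is defined as all patients who received at least one dose of rhC1-INH", and "The Safety Population will be used for all safety analyses". Protocol 11.4.1 agrees: "The Safety Population is defined as all patients who received at least one dose of rhC1INH". Protocol 5.4 nevertheless sets a comparative aim: "The study will evaluate the safety of rhC1INH in the setting of COVID-19 infections if added to SOC compared to SOC treatment only".

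**The concern.** For SpO2, worst has a natural direction. For blood pressure and heart rate it does not: one patient's worst reading may be a low and another's a high. Averaging such values mixes two quantities, and a fall in some patients can be offset by a rise in others.

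A mean with its spread and range also does not tell a safety reader how many patients in each arm had a low or a high value on a given day. In an open-label trial, a count taken from recorded measurements is a useful complement to adverse events, which reach the tables only when an unblinded investigator reports them. If standard-of-care patients have no column, even a complete count in the treated arm has nothing to be set against.

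**Working it through.** The plan gives no figure to reproduce here, so the check is whether the planned statistics determine the number of patients with extreme values.

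**Inputs.** n = 80 is the planned rhC1INH group (Protocol 11.2). The systolic values are assumptions for illustration: k patients at 80 mmHg, k at 170 mmHg, and the other 80 − 2k lying symmetrically about 125 between 95 and 155, with SD s about 125.

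**Mean.**
- k = 1: (80 + 170 + 78 × 125)/80 = 10,000/80 = 125.
- k = 4: (4 × 80 + 4 × 170 + 72 × 125)/80 = 10,000/80 = 125.

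By symmetry the median is 125 in both cases. The minimum is 80 and the maximum 170 in both.

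**SD.** SD² = [(80 − 2k)s² + 2k × 45²]/79.

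| s | k = 1 | k = 4 |
|---|---|---|
| 8 | √[(78 × 64 + 4,050)/79] = 10.7 | √[(72 × 64 + 16,200)/79] = 16.2 |
| 12 | √[(78 × 144 + 4,050)/79] = 13.9 | √[(72 × 144 + 16,200)/79] = 18.3 |
| 15 | √[(78 × 225 + 4,050)/79] = 16.5 | √[(72 × 225 + 16,200)/79] = 20.3 |

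At a given s only the SD moves, but a reader does not know s. Take k = 4 with s = 12, for which the bracket is 26,568. With k = 1 the same bracket needs s² = (26,568 − 4,050)/78 = 288.7, so s = 17.0. That is attainable within 95 to 155, because a uniform spread over ±30 has SD 30/√3 = 17.3. These two data sets then agree on all six planned statistics, while the proportions in each direction are 1/80 = 1.3% and 4/80 = 5.0%.

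**Without cancellation.** Four patients at 80 and none high lower the mean by 4 × 45/80 = 2.25 mmHg. A fall of 2.25 mmHg in every patient does the same. The minimum shows that at least one low value exists, not how many.

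**What a count could support.** Exact 95% intervals are 1.4% to 12.3% for 4/80 and 0% to 8.8% for 0/40. They overlap, so the table would be descriptive.

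**Standard-of-care column.** The planned control arm is 40 of 120 patients: 40/120 = 33% fall outside the Safety Population as worded.

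**The case against.** The strongest reply is that this is an optional extra. SAP 14.6 bases safety mainly on treatment-emergent adverse events, and a six-statistic summary of vital signs is an ordinary descriptive plan for a small Phase 2a pilot. Protocol 10.1.1 defines an adverse event broadly enough to include any unfavourable sign, and Protocol 9.1.4.1 requires conditions that start or worsen after consent to be documented. Events are graded by CTCAE, can halt enrolment (Protocol 10.1.4), and are counted by preferred term and treatment group. Protocol 8.6 reports no earlier effect on vital signs. The blinded data review may add outcomes and populations (SAP 14.2), and CRF instructions may already define worst.

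Much of this stands, and it keeps the point small. It does not close the gap. The explicit rule for turning abnormal values into adverse events covers laboratory findings (Protocol 9.1.4.2). The vital-signs section (9.1.4.3) has no counterpart, and investigators are unblinded (6.2.2). Blinded review can add a table, but it cannot recover readings that were never recorded.

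It is also fair to say that the illustration uses equal numbers of lows and highs, and that minimum and maximum flag the presence of extremes. Equal numbers are needed to hold the mean fixed, not for the count to be hidden.

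On the population, SAP 14.2 analyses by treatment actually received and SAP 14.6 refers to each treatment group, so a standard-of-care column is probably intended. The definition still contradicts that intention and should be corrected.

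**Conclusion.** The point holds as a cheap improvement to the safety reporting. For blood pressure and heart rate, opposite extremes can cancel in the mean, and the number of patients with low or high values cannot be recovered from the planned statistics. Read literally, one third of randomised patients also have no column in this summary. The illustration rests on assumed blood pressures. The conclusion needs only that direction is undefined and that no count is planned, and both can be read from the text.

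Three stronger readings are not supported:

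- A reader might infer that haemodynamic reactions would go unseen. They would not: those reported as adverse events are counted per group, and a shift common to most patients would show in the mean.
- A reader might want to say what share of excursions is lost, or how often patients switch direction between days. The documents give neither the within-day spread nor the rule sites apply, so no such figure can be defended.
- A reader might infer that change from baseline is distorted by post-dose readings on Day 0. For that visit, Protocol 9.2.1 lists "Assessment of vital signs including respiratory rate" ahead of the dosing entry, which favours a pre-dose reading.

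The primary analysis is not affected.

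**What to change.** 1. In SAP 14.6.1 add one descriptive table for systolic blood pressure, diastolic blood pressure and heart rate: the number and percentage of patients below a pre-set lower limit and, separately, above a pre-set upper limit. Present it by treatment group and study day rather than by visit, since Visit 5 covers Days 3 to 13, and give each day's denominator.
2. Include standard-of-care patients explicitly, and align the Safety Population wording with that.
3. In footnote 7 state how worst is chosen for these signs. For example, a reading outside a limit takes precedence, and the low one is kept if both limits are crossed on the same day. Low counts are then complete, and high counts lose only the days on which both limits are crossed.

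**Cost.** One extra table, and a small wording change to the protocol footnote and the CRF instructions; no new measurement. Counts from values recorded before the change are lower bounds and should be labelled so. Denominators will shrink as patients are discharged. The adverse-event tables stay as the main safety analysis.

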14.6.1 Adverse events

Adverse events will be coded according to MedDRA. The assessment of Safety will be based mainly on the frequency of AEs that are treatment emergent (TEAEs). Formal statistical tests will not be conducted for differences in safety parameters between treatment groups.

The incidence of all treatment-emergent AEs will be tabulated after grouping by system organ class and preferred term. For each preferred term and summarized over each system organ class overall, the table will present the absolute number and proportion (%) of patients in each treatment group in whom the event occurred. The incidence of all suspected-IMP-related AEs will be tabulated similarly. The incidence of all treatment-emergent AEs will also be tabulated by severity categories.

Safety will also be summarized with respect to vital signs as mean levels by visit and change from baseline. Abnormal observations on physical examinations will be listed.

Summary statistics for the absolute vital sign value and the changes from baseline will be presented using n, mean, standard deviation, median, minimum, and maximum.

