As per last the Investigator's Brochure, expected adverse reactions are described as follows: The clinical development program supporting safety of rhC1INH is based on a total number of 268 unique patients (up to Oct 2019). Those 268 patients received a combined total of almost 1600 administrations of rhC1INH. The treatment emergent adverse events (TEAEs) that occurred with onset within 7 days of treatment with rhC1INH that were most frequently reported (observed in $\geq 3\%$ of patients treated with rhC1INH) were headache (11%), nausea, and

diarrhea (3% each). There was no evidence of an increase in the percentages of patients with TEAEs or related TEAEs, or in the seriousness or severity of TEAEs, with increases in rhC1INH dose, treatment of a larger number of attacks, and/or treatment of a single attack with an additional dose.

As described in the US prescribing information for rhC1INH, AEs of headache, sneezing, angioedema, erythema marginatum, skin burning sensation, back pain, C-reactive protein increased, fibrin D-dimer increased, vertigo, lipoma, nausea, and diarrhea occurred in $\geq 2\%$ of rhC1INH -treated patients. Note that AEs are listed in the US prescribing information regardless a causal relationship with rhC1INH. The frequency of adverse reactions listed above is defined using the following convention:

- Very common ($\geq 1/10$),
- Common ($\geq 1/100$ to $< 1/10$),
- Uncommon ($\geq 1/1,000$ to $< 1/100$),
- Rare ($\geq 1/10,000$ to $< 1/1,000$),
- Very rare ($< 1/10,000$),

Specific antidotes against rhC1INH do not exist. In the unlikely event of an allergic reaction, standard treatment regimens indicated by the clinical situation (e.g. epinephrine, antihistamines, corticosteroids, etc.) will be administered.

The level of risk may evolve over time, during the study: consequently, a Data Safety Monitoring Board (DSMB) will monitor the safety of all patients, as well as the continuing validity and scientific merit of the study.

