9.1.4 Assessment of Safety Outcomes

9.1.4.1 Adverse events

Participants will be followed for adverse events and outcomes for 3 months post treatment (Day 0). Assessments will be done daily while in the hospital and via a weekly follow-up telemedicine interview or telephone call after discharge.

Adverse events and clinical course including death within 4 weeks will be assessed by a weekly telemedicine or structured telephone interview for 3 months post-treatment. If necessary, medical charts will be reviewed, discharge summaries will be reviewed, or the patients' general practitioner will be contacted regarding specific follow-up information.

Every effort will be made to contact the trial subject and obtain complete data for follow-up. Conditions that started before signing informed consent will be recorded as medical history. Conditions that started or deteriorated after signing informed consent will be documented as AE. Definition of AE and SAE will be found in Section 10.

All AEs will be assessed and documented by the Investigators according to seriousness, intensity, causal relationship with study treatment, action taken with study treatment (e.g. withdrawal), specific treatment for AE and outcome. In addition, time of onset and AE duration will be recorded. Procedures are defined in Section 10. AEs will be recorded on the respective CRF pages. Participants will be asked about any new events/complaints during the hospitalization and up to 3 months post treatment. In addition, participants are asked to report any new events including hospital admission to the study team.

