10.1.1 Definition and Assessment of (Serious) Adverse Events and Other Safety Related Events

An **Adverse Event (AE)** is any untoward medical occurrence in a patient or a clinical investigation participant administered a pharmaceutical product, and which does not necessarily have a causal relationship with the study procedure. An AE can therefore be any unfavorable and unintended sign (including an abnormal laboratory finding), symptom, or disease temporally associated with the use of a medicinal (investigational) product, whether or not related to the medicinal (investigational) product. [ICH E6 1.2]. Any medical conditions

present before signing the informed consent will be reported in the medical history. Any AEs that occur between screening and first treatment are considered as Non-Treatment Emergent Adverse Events (TEAE).

A Serious Adverse Event (SAE) is classified as any untoward medical occurrence that:

- results in death,
- is life-threatening,
- requires in-patient hospitalization or prolongation of existing hospitalization,
- results in persistent or significant disability/incapacity, or
- is a congenital anomaly/birth defect.

In addition, important medical events that may not be immediately life-threatening or result in death, or require hospitalization, but may jeopardize the patient or may require intervention to prevent one of the other outcomes listed above should also usually be considered serious. [ICH E2A]. The EMA Important Medical Events (IME) list will be used as a reference for this.

An elective or pre-planned hospital admission will not be considered as a SAE.

Note: an AE or adverse drug reaction is considered “life-threatening” if, in view of either the Investigator or Sponsor, its occurrence places the patient at immediate risk of death. It does not include an event that, had it occurred in a more severe form, might have caused death. SAEs should be followed until resolution or stabilization. Participants with ongoing SAEs at study termination (including safety visit) will be further followed up until recovery or until stabilization of the disease after termination.

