5.3 Safety variables

The study will evaluate the safety of rhC1-INH in the setting of COVID-19 infections if added to SOC compared to SOC treatment only by measuring the incidence of adverse events up to 3 months post treatment. Moreover, vital signs, physical examinations, and laboratory variables will be assessed for safety.

- Adverse events.
- Physical examination.

	Trial Substance:	Ruconest®	Study No.: C1 6201 PROTECT-COVID-19-US
	Short Title:	Ruconest®: Prevention of severe SARS-CoV-2 infection in hospitalized patients with COVID-19	Sponsor: Pharming Technologies B. V.

A brief, general physical examination will be performed at all visits. Examination will include: height, body weight, eyes, ears/nose/throat, cardiovascular, respiratory, gastrointestinal, genitourinary, musculoskeletal, neurological and psychiatric according to the state of the art.

- Vital signs.

Vital signs will be measured at Visit 2, 3, 4, 5, and 6:

- Heart rate
- Respiratory rate
- Temperature
- Blood pressure (BP_s, BP_d)
- SpO₂.

- Pregnancy.

A serum hCG pregnancy test will be performed at screening in women who may become pregnant, are sexually active, and do not use adequate contraceptive measures.

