5.5 Treatment exposure and compliance

RhC1-INH (Ruconest®) will be supplied by the production company Pharming Technologies, B.V., the Netherlands. RhC1-INH is a recombinant analogue of human C1-INH for intravenous injection. The primary and secondary structures of the molecule and target protease selectivity are consistent with those of plasma-derived C1-INH. RhC1-INH is purified from the milk of transgenic rabbits, and supplied as a sterile, preservative-free, white/off-white lyophilized powder for reconstitution for injection. RhC1-INH contains less than 0.002% of rabbit-related impurities. One international unit (U) of rhC1-INH activity is defined as the equivalent of C1-INH activity present in 1 mL of pooled normal plasma. Each vial of RhC1-INH contains 2100 U of rhC1-INH, 937 mg of sucrose, 83.3 mg of sodium citrate dihydrate and 1.0 mg of citric acid monohydrate. After reconstitution with 14 mL of sterile water for injection, each vial of rhC1-INH contains 150

	Trial Substance:	Ruconest®	Study No.: C1 6201 PROTECT-COVID-19-US
	Short Title:	Ruconest®: Prevention of severe SARS-CoV-2 infection in hospitalized patients with COVID-19	Sponsor: Pharming Technologies B. V.

U of rhC1-INH per 1 mL in a 20 mM sodium citrate buffer with a pH of 6.8. rhC1-INH does not contain preservatives and each vial is for single use only. After randomization, a pharmacist will open the respective sealed boxes, will reconstitute the respective number of rhC1-INH vials and prepare the study medication. RhC1-INH is for intravenous use only. The reconstituted solution is administered as a slow intravenous injection over approximately five minutes. Recommended doses of rhC1-INH for the treatment of an acute angioedema attack are 50 U/kg if body weight <84 kg and 4200 U if >84 kg. A second dose may be administered at the same recommended dose level within a 24-hour period. In this study, we will not use the product according to the licensed indication.

RhC1INH will be administered (150 U/ml) at a 50 U/kg dose (max dose of 4200 U) as a slow i.v. injection every 12 hours for 4 days: a total of 8 doses will be administered.

A market batch will be used for the study.

Participants in the control arm will receive SOC treatment according to local guidelines.

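### Treatment-emergent AEs have no end of window and no split by period, so an excess confined to the 4-day treatment period can be diluted in a table covering up to 3 months

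*SAP*

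**What the plan says.** **The table.** SAP 14.6 and 14.6.1 (and Protocol 11.4.5) rest the safety assessment mainly on treatment-emergent AEs. SAP 14.6.1 says: "The incidence of all treatment-emergent AEs will be tabulated after grouping by system organ class and preferred term". For each term, "the table will present the absolute number and proportion (%) of patients in each treatment group in whom the event occurred". The statistic is a proportion of patients, with no time window and no person-time rate. The tables of suspected IMP-related events and of severity carry no window either.

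**The window.** The SAP does not define treatment-emergent. The only rule is in Protocol 10.1.1, and it fixes a start: "Any AEs that occur between screening and first treatment are considered as Non-Treatment Emergent Adverse Events (TEAE". No end is given in either document.

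**Exposure and collection.** SAP 5.5 gives dosing as "every 12 hours for 4 days: a total of 8 doses will be administered", and Protocol 8.2.1 and 8.6 give a half-life of 2.5 hours. SAP 5.3 describes the safety evaluation as "measuring the incidence of adverse events up to 3 months post treatment", in line with Protocol 5.4: "by measuring the incidence of adverse events up to 3 months post-treatment". On contact frequency, Protocol 9.1.4.1 says: "Assessments will be done daily while in the hospital and via a weekly follow-up telemedicine interview or telephone call after discharge". The same section has the onset time and duration of each AE recorded.

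**Two related statements.** SAP 14.2 and Protocol 11.4.1 restrict the Safety Population to patients dosed with rhC1INH and use it for every safety analysis. The safety objective in SAP section 4 gives a follow-up of four weeks, not 3 months, and SAP section 3 places Visit 7 at week 4 ± 3 months.

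**The concern.** As written, an event on Day 80 counts in the same cell as an event on Day 1. If rhC1INH causes an acute excess, it should appear during or soon after dosing. The table adds about 12 further weeks of events from the illness, its complications and intercurrent conditions, which are unrelated to a drug that has been cleared. An excess in the first days is then expressed as a share of a larger total.

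At stake is the trial's main safety display. The aim in Protocol 5.4 is to compare rhC1INH plus SOC with SOC alone, and a reader who sees similar percentages over 3 months may take that as reassurance about the treatment period. The switch from daily to weekly contact also means that the two parts of follow-up are not ascertained alike, which is a further reason not to show them only as one figure.

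**Working it through.** The documents give no background AE risk for this population and no figure for dilution, so there is no plan figure to reproduce. The rates below are assumptions. The 4 days, the 3 months (13 weeks), the four weeks and the 80 v 40 allocation come from the documents.

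**Formula.** Let p be the control risk for a term inside the early window and q the control risk after it. Let the drug double the risk in the window only.

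- Control, pooled: 1 − (1 − p)(1 − q)
- Active, pooled: 1 − (1 − 2p)(1 − q)
- Absolute excess, pooled: p(1 − q), against p inside the window

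**Illustration: background 1% per week, doubled in week 1.**

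| Table | Active | Control | Ratio |
|---|---|---|---|
| Week 1 only | 2.0% | 1.0% | 2.0 |
| 13 weeks | 1 − 0.98 × 0.99^12 = 13.1% | 1 − 0.99^13 = 12.2% | 1.07 |
| 13 weeks, half of later events detected | 1 − 0.98 × 0.995^12 = 7.7% | 1 − 0.99 × 0.995^12 = 6.8% | 1.14 |
| 4 weeks | 1 − 0.98 × 0.99^3 = 4.9% | 1 − 0.99^4 = 3.9% | 1.25 |

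**Absolute excess and noise.** The 13-week excess is 0.01 × 0.99^12 = 0.89 points, against 1.0 point in week 1. With 80 v 40 patients:

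- Week 1: standard error = √(0.02 × 0.98/80 + 0.01 × 0.99/40) = 2.2 points; excess/standard error = 1.0/2.2, about 0.45.
- 13 weeks: standard error = √(0.131 × 0.869/80 + 0.122 × 0.878/40) = 6.4 points; excess/standard error = 0.89/6.4, about 0.14.

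**Sensitivity to the background.** With p = 5%, the pooled ratio depends on the assumed later risk q:

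| q | 0 | 5% | 10% | 20% | 30% | 50% |
|---|---|---|---|---|---|---|
| Ratio | 2.0 | 1.49 | 1.31 | 1.17 | 1.10 | 1.05 |

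Over an assumed grid of p from 1% to 30% and q from 0 to 60%, the ratio runs from 1.01 (p = 1%, q = 60%: 60.8% v 60.4%) to 2.0 (any p with q = 0). With a constant event rate and a risk window of 4 days in 90, it is 1.04 at p = 1% and 1.02 at p = 5%. The absolute excess loses more when later events are common: at p = 5% and q = 30% it is 5% × 0.70 = 3.5 points instead of 5.

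**The case against.** The strongest reply is that the effect is smaller and less certain than a single ratio suggests. Most of that stands.

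- A reader might infer that a doubled risk will come out near 1.1. The documents do not support any one figure, because they give no background rate. Events in acutely ill inpatients may well cluster early. A term with no later background, such as an acute allergic reaction under its own preferred term, is not diluted at all.
- A reader might infer that the pooled table hides an excess which an early table would reveal. The table reports counts and percentages, and in the illustration the excess hardly shrinks. The early table is also sparse: 80 × 2% = 1.6 expected patients v 40 × 1% = 0.4, and the SOC arm has no event with probability 0.99^40 = 67%. No formal safety tests are planned, so no error rate is affected.
- A reader might infer that earlier discharge in one arm would create a false difference in AE incidence. The mechanism is possible, since assessment becomes weekly at discharge and days hospitalized is a secondary endpoint. However, its size and direction cannot be derived from the documents. The contact schedule is the same in both arms, and Protocol 9.1.4.1 adds chart review, contact with the general practitioner where needed, and patient reporting. Weaker late detection also lessens the dilution (1.14 against 1.07).
- A reader might treat the programme rates in Protocol 3.7, for events "that occurred with onset within 7 days of treatment with rhC1INH", as a benchmark that the trial table must match. Neither document plans that comparison, and those patients were a different population.

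The DSMB review and the halting rules in Protocol 10.1.4 do not depend on this table. None of this supplies the missing end of window or a split by period.

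**Conclusion.** The point holds as one about the design and reading of the safety tables. Treatment-emergent has a start but no end, no table separates the treatment period from later follow-up, and 4 days of dosing are set against up to 3 months of collection. Dilution of the ratio towards 1 follows whenever background events occur after the early window. On the illustrative rates the ratio falls from 2.0 to 1.07 (1.14 with half detection later, 1.25 at four weeks), with a range of 1.01 to 2.0 over other assumed backgrounds. In the same illustration the excess relative to its standard error drops from about 0.45 to 0.14; neither value would be evidence in a trial of this size.

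Two neighbouring defects bear on the remedy. As the Safety Population is worded, SOC-only patients are excluded, so the table has no comparator column; and with no first dose, those patients also have no start for treatment-emergent. The SAP's two follow-up horizons, four weeks and 3 months, give different degrees of dilution and cannot both apply.

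The documents do not support going further and replacing the 3-month incidence as the main result. Three months is the stated safety outcome, and the case is for adding the split beside it.

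**What to change.** In SAP 14.6.1:

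1. Count AEs from Day 0/randomisation in both arms and state when the early period ends.
2. Using recorded onset times, tabulate the treatment period (for example Day 0 to Day 7, with the sponsor justifying the cut-off) and later onset separately, each with its denominator, alongside the 3-month total.
3. Keep SAEs and deaths over full follow-up.
4. Include SOC patients in the Safety Population in SAP 14.2 and Protocol 11.4.1, so that a between-arm table exists.
5. Reconcile the four-week follow-up in SAP section 4, and the Visit 7 timing in SAP section 3, with the 3 months in SAP 5.3.

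The cost is SAP wording, a matching correction to the protocol's Safety Population and a few more safety tables. No new data are needed. One limit remains: patients discharged before the cut-off will have some weekly ascertainment inside the early window, which a footnote should say.
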